3.2.3. Exploratory Endpoints

- Percent change from Baseline in the sum of the areas of all target tophi at scheduled visits, among subjects with ≥ 1 target tophus at Baseline.
- Proportion of subjects who experienced complete resolution of at least 1 target tophus at any time during study, among subjects with ≥ 1 target tophus at Baseline.
- Functional impairment assessed employing the Sheehan Disability Scale (SDS; individual domains as well as total functional impairment) at last on-study visit.
- Work productivity as assessed employing the Work Productivity and Activity Questionnaire: Specific Health Problem (WPAI:SHP; absenteeism, presenteeism, work productivity loss, and activity impairment) at last on-study visit.
- Health status as assessed employing the EuroQol Five Dimensions Questionnaire 3 level (EQ-5D-3L; both descriptive system and visual analogue scale) at last on-study visit.
- Proportion of subjects with gout flares at each 3-month interval during the study period.

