2. STUDY OBJECTIVES

The objectives of this study are as follows:

Primary Objective:

- To evaluate the safety over 24 months of lesinurad 200 mg once daily (qd) when used in combination with a xanthine oxidase inhibitor (XOI), compared with XOI alone, in subjects with gout and moderate renal impairment (estimated creatinine clearance 30 to <60 mL/min) who have not reached target serum uric acid (sUA) levels on an XOI alone.

Efficacy Objective:

- To evaluate the efficacy over 24 months of lesinurad 200 mg qd in combination with an XOI, compared with XOI alone, in subjects with gout and moderate renal impairment who have not reached target sUA levels on an XOI alone.

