6.10.4. Gout Flares

Acute gout flares occur when monosodium urate crystals in the joint(s) cause acute inflammation. A flare is characterized by pain, redness, swelling, and warmth lasting days to weeks. Pain may be mild or excruciating. Most initial attacks occur in lower extremities. The typical presentation in the metatarsophalangeal joint of the great toe (podagra) is the presenting joint for 50% of people with gout (<http://www.cdc.gov/arthritis/basics/gout.html>, accessed 6 October 2016).

Gout flares will be recorded on the CRF, including information regarding the start and stop date; patient-reported severity (mild/moderate/severe); and the treatment that was required, if any. Medications used for gout flare treatment will be documented on the concomitant medications CRF.

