8.3.1. Day 1 (1 Day After Baseline Visit)

This is not a study visit. Subjects will receive study-supplied medications (IP, XOI, and colchicine, as applicable) at their Baseline Visit and will start taking these medications at home on Day 1 (1 day after Baseline Visit). Colchicine may be taken at Baseline. All study-supplied medications should be taken in the morning. Refer to [Section 5.3](#) for details on administration of study-supplied medications.

8.3.2. Month 1 (Day 28 ±7 Days) and Months 3 Through 21 (Visits Every 3 Months ±7 Days)

The following procedures and assessments will be performed at each visit, except where otherwise noted:

- Administer patient-reported outcome assessments (except at Month 1).
- Review gout flares that occurred since the last study visit.
- Take vital signs.
- Assess AEs.
- Record concomitant medications.

- Assess compliance with IP (lesinurad/placebo).
- Assess compliance with XO1.
- Assess compliance with gout flare prophylaxis (Months 1, 3, and 6).
- Measure target tophi (Months 6, 12, 18).
- Collect blood sample for hematology (Months 6, 12, and 18).
- Collect blood sample for the following serum chemistry analyses:
 - Analytes 1.
 - Analytes 2.
 - Analytes 3 (Months 6, 12, and 18).
 - Pregnancy test for women of childbearing potential (Month 12).
- Collect blood sample for plasma biomarkers (Months 6, 12, and 18).
- Collect urine sample for the following analyses:
 - Urinalysis.
 - Protein-creatinine ratio (Months 6, 12, and 18).
 - Urine biomarkers (Months 6, 12, and 18).
- Except at Month 1, dispense IP (lesinurad or placebo), XO1, and colchicine (as needed at Month 3).

For subjects that have permanently discontinued IP, maintaining the visit schedule is recommended. Although all assessments are encouraged, at a minimum, it is requested that collection of AEs and collection of a blood sample for Analytes 1 occur.

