9.1. General Considerations

All subjects will be randomized to either lesinurad 200 mg or matching placebo in combination with an XOI in a 1:1 ratio and stratified by the following stratification factors:

- Screening eCrCl: the average eCrCl of Screening Visit 1 and Screening Visit 2 (30.0 to <45.0 mL/min or 45.0 to <60.0 mL/min).
- Baseline measurable target tophus status: present or absent.
- Type of XOI: allopurinol or febuxostat.

This study will enroll approximately 50% of subjects with eCrCl 30.0 to <45.0 mL/min and approximately 50% with eCrCl 45.0 to <60.0 mL/min. There is no planned sample size requirement on the number of subjects enrolled by type of XOI or Baseline tophus status. However, a stratification variable (eg, Baseline measurable target tophus status [present/absent]) may be dropped from the stratified analysis (eg, mixed model repeated measures [MMRM] or Cochran Mantel Haenszel [CMH]) if the number of subjects in any stratum is very low (eg, <10% of total subjects). The decision to drop a stratification variable will be made prior to database lock and will be documented in the SAP.

All safety and efficacy data will be listed and summarized by treatment group.

Baseline is defined as the last observed measurement prior to the first dose of IP, unless otherwise specified.

Descriptive statistics will consist of the number of subjects (n), mean, standard deviation (SD), median, minimum, and maximum for continuous variables, and counts and percentages for categorical variables.

Unless otherwise specified, all confidence intervals (CIs) will be calculated at the 95% level and all hypothesis tests will be performed at the 0.05 level. All analyses including summaries and listings will be performed using SAS[®] software version 9.1 or higher.

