9.4.4. Exploratory Endpoints

For all exploratory endpoints, descriptive statistics will be provided at each scheduled visit.

For percent change from Baseline in the sum of target tophi area among subjects with target tophus at Baseline, the between-treatment difference will be assessed using similar MMRM analysis as appropriate as in [Section 9.4.2.1](#).

For the proportion of subjects with target tophi at Baseline who experience complete resolution of at least 1 target tophus at any time during study, the between-treatment difference in tophus resolution rates in this subset of subjects will be assessed using the CMH test statistic, stratified by type of XOI, and Screening eCrCl (as appropriate as stated in [Section 9.1](#)). Results will be summarized by randomized treatment group and expressed as proportions and corresponding adjusted 95% CI of the difference between response rates.

The proportion of subjects reporting gout flares will also be summarized at each visit.

The patient-reported outcomes (ie, SDS, WPAI:SHP, and EQ-5D-3L) will be summarized by visit (Visits 3, 6, 9, . . . 24). In addition, the mean score at last on-study visit will be analyzed using analysis of covariance (ANCOVA), which include terms for treatment stratification factors (as appropriate as stated in [Section 9.1](#)) and Baseline patient reported outcome value as covariate.

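### No between-arm estimate of gout flares is pre-specified: dated, repeated flares are summarised only as separate interval proportions that are never combined

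*Combined protocol and SAP*

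**What the plan says.** - **Data.** Section 6.10.4: "Gout flares will be recorded on the CRF, including information regarding the start and stop date". Severity and treatment are recorded too. Each post-Baseline visit includes the item "Review gout flares that occurred since the last study visit" (section 8.3.2, and likewise 8.3.3 to 8.4.2).
- **Endpoint.** Section 3.2.3, the last exploratory item: "Proportion of subjects with gout flares at each 3-month interval during the study period".
- **Analysis.** Section 9.4.4 has a general rule, "For all exploratory endpoints, descriptive statistics will be provided at each scheduled visit", and one flare-specific sentence, "The proportion of subjects reporting gout flares will also be summarized at each visit". Section 9.1 adds that "All safety and efficacy data will be listed and summarized by treatment group", so the proportions will appear by arm.
- **Neighbouring endpoints in 9.4.4.** For tophus area, "the between-treatment difference will be assessed using similar MMRM analysis as appropriate as in" section 9.4.2.1. Tophus resolution gets a CMH comparison with an adjusted 95% CI. The patient-reported outcomes get an ANCOVA with treatment as a term.
- **Elsewhere.** Section 6.11.1 keeps flares off the AE form unless they are serious, so AE tables will not supply a flare comparison. Section 9 defers further detail to a SAP, but the documents contain no SAP text on flares.

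**The concern.** The efficacy objective is "To evaluate the efficacy over 24 months of lesinurad 200 mg qd in combination with an XOI, compared with XOI alone". Sections 1.2.3 and 1.3 explain that starting urate-lowering therapy can provoke flares, so an effect in either direction is of interest. The planned output is a row of percentages per arm for each of eight intervals, with no single estimate of the treatment effect and no measure of its uncertainty. A reader would have to compare the arms by eye, one interval at a time, and each interval holds only a small part of the flare information. Any overall flare comparison would have to be chosen after unblinding, when it is less credible. The protocol names a between-arm method for the other exploratory endpoints, so the gap is specific to flares.

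The two descriptions also differ. Section 3.2.3 speaks of 3-month intervals and 9.4.4 of visits, which include Month 1.

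**Working it through.** **The plan's own figures.** None is stated for flares. The sizing in 9.2 reproduces with 300 per arm: 1.96 × 10 × √(2/300) = 1.60 mL/min for eCrCl, and power of 98.6% overall and 83.2% with 150 per arm in a stratum for 20% versus 35%. So 300 per arm is the right base.

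**Inputs from the documents.** 300 per arm; a study month is 28 days (section 8). One interval is 84/365.25 = 0.230 years. Month 6 to Month 24 is 504/365.25 = 1.380 years.

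**Assumed inputs, not in the documents.** Placebo rate 0.5 to 1.5 flares per year; gamma-Poisson counts with dispersion k of 1 to 3; rate ratio 0.6 or 0.7; 25% leaving uniformly over Month 6 to 24, so mean follow-up is (0.75 + 0.25 × 0.5) × 1.380 = 1.207 years; two-sided 5%.

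**Worked example: 1.0 per year, k = 2, rate ratio 0.6.**

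1. *One interval.* P(any flare) = 1 − (1 + kλ)^(−1/k). Placebo, λ = 0.230: 17.2%. Lesinurad, λ = 0.138: 11.5%. Two-proportion power is 52% with all 300 per arm present and 41% with the 225 per arm who complete. Simulation with dropout gives 46% in the first interval and 42% in the last.
2. *Any flare over 18 months.* The same formula at the mean follow-up gives 45.9% versus 36.1%, power 68% (simulation 63%).
3. *Negative binomial rate ratio.* Mean counts are 1.207 and 0.724. Var(log ratio) = (1/1.207 + 2 + 1/0.724 + 2)/300 = 0.0207, SE 0.144. Then 0.511/0.144 − 1.96 = 1.59, power 94% (simulation 95%).

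**Simulated power (%), 300 per arm, Month 6 to 24.** Columns 2 to 4 come from one simulation (400 replicates; Monte Carlo standard error up to √(0.25/400) = 2.5 points). The last column comes from a separate one (2000 replicates, subject-level robust variance).

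| Rate ratio, rate per year, k | One interval (last / first) | Any flare, 18 months | Negative binomial | Counts vs all interval flags jointly |
|---|---|---|---|---|
| 0.6, 0.5, 1 | 30 / 42 | 78 | 94 | 93 vs 91 |
| 0.6, 1.0, 2 | 42 / 46 | 63 | 95 | 94 vs 90 |
| 0.6, 1.5, 3 | 39 / 48 | 48 | 87 | 89 vs 81 |
| 0.7, 0.5, 3 | 16 / 18 | 28 | 45 | 48 vs 45 |
| 0.7, 1.0, 2 | 25 / 26 | 38 | 73 | 68 vs 62 |

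Over the full grid, one interval has 16% to 69% power and the rate model 45% to 100%. Type I error was about 5% for the tests in columns 2 to 4. The last column shows gaps of 2 to 8 points; a repeat run put the largest at 9.

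**Where the loss arises.** For Poisson counts, a yes/no flag keeps λ/(e^λ − 1) of the information on the log rate. At 1 flare per year this is 0.230/(e^0.230 − 1) = 0.89. All eight flags together therefore keep 89%, while one flag alone carries 0.89/8 = 11% of the 24-month information. At 0.5, 2 and 4 flares per year the joint figures are 94%, 79% and 61%. More than half is lost only above about 5.5 per year.

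**Second setting.** With 24 months, no dropout, rate ratio 0.75 and 1 flare per year, power for k = 0, 1 and 2 is 99%, 79% and 58% for the rate ratio, against 32%, 26% and 22% for one interval. With 210 per arm (30% loss) the rate ratio has 96%, 64% and 44%.

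**The case against.** The strongest reply is that flares are the last exploratory item, the trial was not sized for them, and descriptive reporting of such an endpoint is legitimate. Interval proportions also show timing, which matters when flares cluster after treatment starts and prophylaxis ends partway through. A 24-month rate ratio could average opposing early and late effects. Section 9 leaves room for the SAP to add detail. Section 9.4.4 plans no flare test at all, so the power figures compare possible analyses and do not measure power lost by a planned test.

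Much of this stands. It sets the severity, and it is why the interval proportions should stay. It does not explain why flares alone among the exploratory endpoints lack a between-arm method.

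Two stronger readings are tempting and should be resisted:

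- *That the yes/no cut throws away most of the flare information.* It does not at plausible rates: analysed jointly, the flags come within about 2 to 9 power points of counts. The loss comes from reading the intervals separately.
- *That the trial cannot say whether lesinurad changes flare rates.* The dated data are collected and will be shown by arm. Only the pre-specified comparison is missing, and the SAP can supply it before unblinding.

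**Conclusion.** The gap holds as stated. Sections 3.2.3 and 9.4.4 combine nothing across intervals and pre-specify no between-arm flare estimate or CI. Under the assumed rates, a single interval is weak (about 16% to 69% power) and a rate model much stronger (about 45% to 100%), mainly because it uses the whole follow-up. Even so, the rate model is not well powered when dispersion is high or the effect modest. Its value is one interpretable estimate with an interval: in the 24-month setting at 1 flare per year, the 95% limits lie a factor of about 1.23 (k = 1) to 1.30 (k = 2) either side of the ratio.

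Flare rate, dispersion, effect and dropout are all assumptions, and only reductions were simulated. Severity is minor, since primary and key efficacy conclusions do not depend on this endpoint.

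**What to change.** In 9.4.4:

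1. Keep the 3-month proportions as descriptive output, and use the same time unit in 3.2.3 and 9.4.4.
2. Add one exploratory analysis, outside the hierarchical procedure of 9.4.3: negative binomial regression of the number of flares per subject from Day 1 to Month 24 in the ITT population. Include treatment and the randomisation factors (subject to the sparse-stratum rule in 9.1), with log flare-observed time as offset. Report the rate ratio with 95% CI.
3. Define flare-observed time from the dates of flare review, and state the rule that separates one flare from the next; 6.10.4 gives none.
4. Report Day 1 to Month 6 and Month 6 to Month 24 rate ratios as supportive. The later one is conditional on still being followed at Month 6, so it should not lead. Nor does Month 6 mark the end of prophylaxis for everyone, since corticosteroid courses may be shorter (5.3.2.2).
5. State a missing-data caveat. After permanent discontinuation of IP, the requested minimum in 5.3.2.1.2 and 8.3.2 is AEs and Analytes 1, without flare review. Flare data may then be incomplete in a way that the offset does not correct.

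The cost is a paragraph of analysis text and a small set of models, with no new data, visits or subjects. The drawback is that the estimate depends on the working model and on how separate flares are counted.

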3.3. Study Duration

The overall duration of the study is anticipated to be approximately 5 years. The total duration of study participation for each subject (from Screening Visit 1 through the last study visit) is anticipated to be up to approximately 26 months.

For regulatory reporting purposes, the end of the study is defined as the date of the last subject's last assessment (scheduled or unscheduled).

4. STUDY POPULATION SELECTION

4.1. Study Population

Approximately 600 subjects will be enrolled (300 per treatment group).

4.2. Inclusion Criteria

Each subject must meet the following criteria to be enrolled in this study.

1. Subject is able to understand the study procedures, the risks involved, and willing to provide written informed consent before the first study related activity.
2. Subject is willing to adhere to the protocol schedule.
3. Subject is ≥ 18 years and ≤ 85 years of age.
4. Subject has a diagnosis of gout.
5. Subject has moderate renal impairment with estimated creatinine clearance (eCrCl calculated by the Cockcroft-Gault formula using ideal body weight) 25.0 to ≤ 65.0 mL/min at Screening Visits 1 and 2 and an average eCrCl for both screening visits of 30.0 to < 60.0 mL/min.
6. Subject has been taking an XOI as urate-lowering therapy (ULT) indicated for the treatment of gout for at least 4 weeks prior to Screening at a stable, medically appropriate dose, as determined by the Investigator. The minimum dose of allopurinol is 200 mg daily, and the minimum dose of febuxostat is the lowest approved dose per the local product label.
7. Subject has a serum uric acid level ≥ 6.0 mg/dL (357 $\mu\text{mol/L}$) at Screening Visits 1 and 2.
8. Subject is male or female; females must not be pregnant or breastfeeding and females of childbearing potential must agree to use non-hormonal contraception during the Screening Period and while taking IP.
9. Subject has a body mass index < 45 kg/m².

4.3. Exclusion Criteria

Subjects who meet the following criterion will be excluded from the study:

1. Subject had unstable angina, New York Heart Association class III or IV heart failure, myocardial infarction, or stroke within the last 6 months prior to randomization; or had a deep venous thrombosis within the previous 3 months prior to randomization.
2. Subject has uncontrolled hypertension (defined as systolic pressure above 160 or diastolic pressure above 95 mm Hg at either Screening Visits 1 or 2).
3. Subject has severe hepatic impairment (defined as Child-Pugh Class C) or is known human immunodeficiency virus (HIV) positive.
4. Subject is a solid organ transplant recipient.

5. Subject has a urine protein of 3+ or higher by dipstick by the central laboratory at Screening Visit 2.
6. Subject has a history of glomerulonephritis.
7. Subject is taking valpromide, progabide, valproic acid, or other known inhibitors of epoxide hydrolase, or subject is taking ranolazine, cyclosporine, azathioprine or mercaptopurine.
8. Subject is receiving chronic treatment with more than 325 mg of salicylates per day.
9. Subject is unable to initiate gout flare prophylaxis with colchicine or low-dose oral corticosteroids at Baseline.
10. Subject is taking any other drug approved for use as a urate-lowering medication other than allopurinol or febuxostat (eg, pegloticase, probenecid, benzbromarone) within 4 weeks prior to Screening or during Screening.
11. For subjects who will be taking colchicine for gout flare prophylaxis: Subject is taking, or anticipated to take during the first 6 months on study, moderate or strong CYP3A inhibitors (ie, verapamil or diltiazem, clarithromycin, and fluconazole; see [Section 7.1.3](#) for more details) or grapefruit or grapefruit juice.
12. Subject previously participated in a clinical study involving lesinurad (RDEA594) or verinurad (RDEA3170) and received active treatment or placebo, or has taken commercially-available lesinurad.
13. Subject has a gout flare during the Screening Period.
14. Subject is pregnant or breastfeeding.
15. Subject consumes more than 14 drinks of alcohol per week (eg, 1 drink = 5 oz [150 mL] of wine, 12 oz [360 mL] of beer, or 1.5 oz [45 mL] of hard liquor).
16. Subject has a history of malignancy and has been on active treatment within the previous 5 years prior to randomization with the exception of non-melanoma skin cancer, treated in situ Grade 1 cervical cancer, or treated ductal carcinoma in situ of the breast.
17. Subject has been hospitalized (other than for elective surgery) or received intravenous contrast (eg, for CT scan or any angiography) within 1 month prior to Screening or during Screening.
18. Subject has participated in a clinical trial within 8 weeks prior to Screening.
19. Subject has any other medical or psychological condition, which in the opinion of the Investigator might create undue risk to the subject or interfere with the subject's ability to comply with the protocol requirements or to complete the study.
20. The maximum number of subjects in the eCrCl stratification subgroup has been reached.

5. STUDY TREATMENT

All subjects will receive IP (lesinurad or matching placebo) and study-supplied XOI (allopurinol or febuxostat), which must be taken in combination. All subjects will also receive colchicine as gout flare prophylaxis through their Month 6 study visit as tolerated. Subjects unable to take colchicine (described in Section 5.2.2.) are permitted to take a short course of low-dose oral corticosteroids.

5.1. Description of Investigational Product

5.1.1. Lesinurad

Lesinurad will be supplied as 200 mg tablets in 100-count high-density polyethylene (HDPE) bottles with induction seals and screw-on polypropylene closures. Lesinurad 200 mg tablets are blue, oval shaped tablets.

5.1.2. Placebo Comparator

Placebo tablets matching the lesinurad 200 mg tablets will be provided by the Sponsor in 100-count HDPE bottles with induction seals and screw-on polypropylene closures.

5.2. Other Study Treatments

Commercially available allopurinol, febuxostat, and colchicine drug product will be used. The relevant product labeling will be provided to Investigators.

5.2.1. Xanthine Oxidase Inhibitors

XOI (allopurinol or febuxostat) tablets will be provided at Baseline based on the individual subject's stable dose during screening. The minimum Baseline dose of allopurinol permitted is 200 mg daily; the minimum Baseline dose of febuxostat is the lowest approved dose per the local product label. The maximum dose of each XOI permitted is the highest approved dose per the local product label. The dose and dosing regimen of XOI should not be changed during the study, unless decreased for toxicity.

5.2.2. Gout Flare Prophylaxis

Gout flare prophylaxis, colchicine, will be provided through the Month 6 study visit. The dose of colchicine will be 0.5 or 0.6 mg qd based on the local label. The frequency may be adjusted based on the local label, medical history of the subject, and clinical judgement (ie, dosed every other day or 3 times a week if needed as appropriate, particularly for subjects with lower eCrCl).

Subjects unable to take colchicine (ie, those who have a documented intolerance or allergy to colchicine or who are taking a concomitant medication contraindicated for use with colchicine [eg, P-gp or strong/moderate CYP3A4 inhibitors, see [Section 7.1.3](#)]) are permitted to take low-dose oral corticosteroids (ie, ≤ 10 mg/day of prednisone, or prednisolone, or their equivalent) for a short course, such as through the Month 3 study visit, at the discretion of the Investigator. The steroid regimen should be individualized for each subject based on the need for gout flare

prophylaxis and potential side effects of persistent corticosteroid use, such as in relation to comorbid conditions.

If IP is permanently discontinued prior to the end of the gout flare prophylaxis period, the gout flare prophylaxis should be discontinued. If IP is interrupted and re-initiated, subjects can re-initiate gout flare prophylaxis at the discretion of the Investigator. Investigators should consider reinitiating gout flare prophylaxis based on the clinical circumstances.

The use of NSAIDs for gout flare prophylaxis is not permitted.

